This will be a randomized-controlled trial 1:1. Randomization to each group will be conducted via the REDCap randomization module.

6. Outcomes:

Our primary outcome is the time in range (via CGM data) during the management of Type 2 diabetes in pregnancy between 34 and 36 weeks gestation. We chose this primary outcome because it is at the time of peak insulin resistance and time in range is more closely associated with pregnancy outcomes as compared to other means of monitoring glucose control.

Secondary outcomes include FitBit data (duration of postprandial walk (in minutes), sleep duration, baseline heart rate, maximal heart rate during walks, frequency of aerobic exercise per week), CGM data (mean glucose level, glucose excursions, fasting blood sugar), total daily insulin dose, fetal demise, fetal growth restriction, preeclampsia, placental abruption, mode of delivery (cesarean or vaginal delivery), indication of cesarean delivery, presence of shoulder dystocia (for vaginal deliveries), quantitative blood loss (QBL mL), postpartum hemorrhage (QBL > 1000 mL), infection (either chorioamnionitis or postpartum endometritis prior to discharge), birth weight (gram), APGAR scores, neonatal infection (defined as sepsis, fever, positive cultures, or a suspicious clinical course that warranted antibiotics treatment), respiratory distress syndrome, necrotizing enterocolitis, and neonatal intensive care unit admission (NICU), and days in NICU. Other secondary outcomes will include metabolomic markers collected from the urine and blood, as well as body composition data.

We will also collect demographic and clinical characteristics including maternal age, gestational age at delivery, race, ethnicity, insurance, marital status, history of preterm birth, parity, and number of previous cesarean or vaginal delivery.

Chart review for secondary outcomes and demographic/clinical characteristics will be completed through Allscripts, EPIC, and Powerchart.

7. Data Gathering and Safety:

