The FitBits, continuous glucose monitors, and all supplies for the patient will be paid for with no cost to the patient or the patient's insurance company. The [name] Discretionary Research Fund is covering the cost of the FitBits and CGMs. For the Dexcom G7, it is recommended that the sensor be changed every 7 days, which will be performed by the patient. Therefore, the sensor will need to be changed between 8 and 37 times throughout the study period, dependent upon what gestational age the patient was enrolled.

The research team will gather the data from the continuous glucose monitors via the share function, similar to how the data is shared to the clinical team.

The primary outcome will focus on the 34 through 36 week gestation data. However, the data from the rest of the subject's participation will be included in the secondary outcomes.

There will be two blood draws: at enrollment and again between 34 and 36 weeks gestation. A urine collection will also be performed at these times. These will be collected at an already scheduled clinic appointment.

Therefore, no additional appointment will be needed for this. It will be drawn by phlebotomy staff or research nurses. It will be kept refrigerated, processed within 24 hours, and kept in -70 degree freezer in a secured area. After collection, samples will be run and kept in a separate repository for potential future use. This will be paid by the [name] Discretionary Research Fund. There will be no cost to the patient.

The study dataset and ID key will be stored in REDCap in separate projects due to inclusion of data from the EMR.

8. Sample size calculation: Time in range in pregnant patients with pre-gestational diabetes is 66.3% with a standard deviation of 21.3% ³. We assume that 20 minutes of postprandial walking after each meal will decrease the mean glucose by 30%. Therefore, assuming a 30% improvement in time in range, with a power of 80% and alpha of 0.05, 18 mother/neonate pairs per group would be needed to reach statistical significance. Assuming a 10% loss to follow up rate, a total of 40 mother/neonate pairs will be included in the study.

9. Statistical analysis: Descriptive statistics will be provided first for describing the subjects' demographic and clinical characteristics. Fisher's exact or Chi Squared test will be used to compare categorical variables and the Student t-test or Man-Whitney U test will be used to compare numerical variables.

References:

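### Mode of delivery is assigned an unadjusted test although previous cesareans are already recorded; stratifying would be a small, free gain in precision, not the correction of an error

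*Protocol*

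**What the plan says.** Section 6 (Outcomes) lists among the secondary outcomes "mode of delivery (cesarean or vaginal delivery), indication of cesarean delivery". Later in the same section, the characteristics to be collected include "history of preterm birth, parity, and number of previous cesarean or vaginal delivery". The number of previous cesareans is therefore known for every woman and is fixed before randomization.

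Section 9 (Statistical analysis) plans descriptive statistics for demographic and clinical characteristics, and then states: "Fisher's exact or Chi Squared test will be used to compare categorical variables". It names no covariate, stratum or model.

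Section 5 (Randomization) says "This will be a randomized-controlled trial 1:1" and "Randomization to each group will be conducted via the REDCap randomization module". It names no stratification factor. The eligibility criteria in section 3 do not exclude women with a previous cesarean.

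The primary outcome is CGM time in range. The sample size in section 8 is built on that outcome alone.

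**The concern.** A previous cesarean plausibly makes another cesarean more likely, for reasons that may have little to do with glucose control. With about 20 women per arm and no stated stratification, one arm may by chance hold several more such women than the other. The unadjusted comparison then carries part of that imbalance into the observed difference in cesarean rate, and nothing in the named analysis removes it. Readers see one realized table, not the average over all possible randomizations. If the imbalance is noticed only afterwards, any adjustment is post hoc. The variable needed to prespecify the adjustment is already being collected.

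**Working it through.** **The plan's own figure.** The only size stated is for time in range. Section 8 gives a mean of 66.3%, SD 21.3% and "assuming a 30% improvement in time in range", which read as relative is 0.30 × 66.3 = 19.89 points. With two-sided alpha 0.05 and power 80%, n = 2 × (1.960 + 0.842)² × 21.3² / 19.89² = 18.00 per group, matching the stated 18 (power at 18 is 79.995%). Then 36 / 0.90 = 40, or 20 per arm. No figure is stated for mode of delivery.

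**Assumed inputs.** The protocol gives no rate of previous cesarean and no cesarean rate. Let π be the proportion with a previous cesarean (20%, 30%, 40%). Let c0 and c1 be the cesarean risks without and with one: 35% and 85% (stronger set), or 30% and 60% (weaker set).

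**Chance of imbalance.** The count in each arm is Binomial(20, π), independently. The probability that the arms differ by four or more women is 16.4%, 22.6% and 25.8% for π = 20%, 30% and 40%.

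**Effect of an imbalance.** Shift in the arm difference = imbalance × (c1 − c0). Four women are 4/20 = 20 points, so the shift is 0.20 × 0.30 = 6 points (weaker set) or 0.20 × 0.50 = 10 points (stronger set). Larger imbalances shift it in proportion.

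**Share of the sampling variance.** With m = π·c1 + (1 − π)·c0, the share is π(1 − π)(c1 − c0)² / [m(1 − m)]. For π = 30% and the stronger set:

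- m = 0.30 × 0.85 + 0.70 × 0.35 = 0.50
- share = 0.21 × 0.25 / 0.25 = 21%
- SD of the unadjusted difference = √(2 × 0.25 / 20) = 15.8 points
- SD due to imbalance = 0.50 × √(2 × 0.21 / 20) = 7.2 points, which is a part of the 15.8 (7.2² / 15.8² = 21%), not an addition to it

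**Gain from stratifying.** The large-sample ceiling on the SD reduction is 1 − √(1 − share). Small strata give back a little. The last column is from simulation (200,000 null trials per row, 20 per arm, Mantel-Haenszel risk difference).

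| π | c0 / c1 | share | ceiling | simulated |
|---|---|---|---|---|
| 20% | 30% / 60% | 6.3% | 3.2% | 2.0% |
| 30% | 30% / 60% | 7.9% | 4.1% | 2.7% |
| 40% | 30% / 60% | 8.9% | 4.5% | 3.3% |
| 20% | 35% / 85% | 16.2% | 8.4% | 6.8% |
| 30% | 35% / 85% | 21.0% | 11.1% | 9.7% |
| 40% | 35% / 85% | 24.2% | 13.0% | 11.6% |

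In the fifth row the SD falls from 15.8 to 14.3 points, so a 95% half-width falls from 1.96 × 15.8 = 31 to 1.96 × 14.3 = 28 points.

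**Type I error.** A separate null simulation used 18 or 20 per arm, π = 20% to 40%, c0 = 30% and c1 = 60% to 90%. Its upper risk is a little above the range used elsewhere here.

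| | Fisher | chi-squared | stratified Mantel-Haenszel |
|---|---|---|---|
| all trials | 2.1–2.8% | 4.4–6.5% | 4.6–5.0% |
| imbalance of 20 points or more | 3.7–8.1% | 7.2–15.9% | not tabulated |

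Mean bias of the unadjusted difference was zero to within 0.001.

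**Power.** With 18 to 20 per arm, unadjusted power is about 22% to 25% for a 20-point difference (50% versus 30%, or 60% versus 40%) and about 9% for 50% versus 40%.

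**The case against.** The strongest reply is that nothing here is wrong. Randomization makes the unadjusted comparison unbiased, overall error is near or below 5%, and chance imbalance is already part of the sampling error the test allows for. All of this stands. A reader might infer that the planned test is biased or invalid; the calculations do not support that.

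Three other strong readings also fail. A large imbalance is not likely: a difference of four or more women is absent in roughly three trials in four, or more. An imbalance does not carry over in full, because it is multiplied by the risk difference between strata (0.3 to 0.5 here). Nor do the documents say that previous cesarean is the strongest predictor of cesarean; that it is prognostic at all is a plausible assumption.

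A second reply is that covariate adjustment of a secondary outcome belongs in a statistical analysis plan, which is not shown. This has weight and limits the point to a suggestion. It does not remove it, because section 9 is not silent: it names the test for all categorical variables, and a later plan that follows it would inherit that choice. Section 9 does not, however, forbid a supportive analysis or confine the collected characteristics to description. The absence of stratified randomization is likewise inferred from silence in section 5.

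Third, the protocol also records the indication for cesarean, which helps a reader recognise repeat procedures. That is a partial mitigation, but it is observed after randomization and does not replace a baseline stratum.

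Finally, mode of delivery is one of many secondary outcomes and stays underpowered after adjustment. That stands too.

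**Conclusion.** The point holds as a minor improvement. The protocol fixes a valid but unadjusted test for mode of delivery while holding a baseline variable that could sharpen it at no cost. Over the assumed rates, about one trial in six to one in four has a four-woman imbalance or more; four women move the cesarean difference by 6 to 10 points, and stratification trims its SD by about 2% to 12%. If previous cesarean is weakly prognostic in this clinic, or if the randomization is in fact stratified on it, the gain is smaller. The primary outcome, the sample size and every stated figure are unaffected, and the cesarean comparison remains exploratory.

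**What to change.** Add to section 9 that mode of delivery will be compared between arms with a Mantel-Haenszel or exact test stratified by previous cesarean (none versus any; women with no previous delivery count as none), with a stratified risk difference and confidence interval. Keep the unadjusted table as description, and label the result exploratory.

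A separate analysis of first cesareans among women with no previous one is optional and not needed; at 30% prevalence it would hold only about 20 × 0.70 = 14 women per arm.

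The cost is a sentence or two of analysis wording. No new data, participants or procedures are required. It should be settled before outcome data by arm are seen.

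### Section 8's 80% power rests on a normal approximation; with the tests named in Section 9, 18 evaluable women per group give about 78% (t-test) or about 75% (Mann-Whitney)

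*Protocol*

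**What the plan says.** Section 8 of the protocol takes its planning values from a cited cohort: "Time in range in pregnant patients with pre-gestational diabetes is 66.3% with a standard deviation of 21.3" (percent). It goes on "assuming a 30% improvement in time in range", and concludes that "with a power of 80% and alpha of 0.05, 18 mother/neonate pairs per group would be needed to reach statistical significance". Loss to follow-up is then added: "Assuming a 10% loss to follow up rate, a total of 40 mother/neonate pairs will be included in the study". Section 5 fixes equal allocation.

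Section 8 does not name the formula, does not say whether alpha is one- or two-sided, and does not say whether the 30% is relative or in percentage points. On analysis, Section 9 says that "the Student t-test or Man-Whitney U test will be used to compare numerical variables". It does not say which of the two applies to time in range, the primary outcome in Section 6.

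**The concern.** A sample size of 18 per group is small enough for the difference between a z-test with known SD and a t-test with estimated SD to show in the power. If 18 came from the z formula and the analysis uses a t-test or a rank test, the trial has less than the stated 80% power even when every planning assumption is true. The planned enrolment could have hidden this if it left a margin, so the loss allowance needs checking too.

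What is at stake is the accuracy of a figure that readers will use to interpret the result, above all a null result. The validity of the comparison is not affected.

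**Working it through.** **Inputs (protocol, Sections 5, 8 and 9).** Control mean 66.3%; SD 21.3 points; improvement 30%; power 80%; alpha 0.05; 1:1 allocation; 18 evaluable per group; 10% loss; 40 enrolled; t-test or Mann-Whitney test.

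**Step 1: reproduce 18.** Read as relative, the improvement is 0.30 × 66.3 = 19.89 points, so d = 19.89/21.3 = 0.934. The two-sided normal approximation gives

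n = 2 × [(1.95996 + 0.84162) × 21.3 / 19.89]² = 18.002 per group.

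The other readings do not return 18:

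| Reading | n per group, z formula |
|---|---|
| Relative 30%, two-sided | 18.00 |
| Relative 30%, one-sided | 14.2, so 15 |
| Absolute 30 points, two-sided | 7.9, so 8 |

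The relative, two-sided reading is therefore used below. It is an inference from the figure, not something that Section 8 says.

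**Step 2: does rounding matter?** By the same z formula, power at exactly 18 per group is 79.995%, so going from 18.002 to 18 costs about 0.005 points. With z values rounded to 1.96 and 0.84, n is 17.98; with the difference rounded to 19.9, n is 17.98; with it rounded to 20, n is 17.80. All three round up to 18.

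**Step 3: power of the t-test.** With n per group, the degrees of freedom are 2n − 2 and the noncentrality is 19.89 / (21.3 × √(2/n)). At n = 18 that is 34 degrees of freedom, noncentrality 2.801 and a critical value of 2.032 (the z formula uses 1.960).

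| Evaluable per group | Power, two-sided t-test |
|---|---|
| 18 | 77.7% |
| 19 | 79.97% |
| 20 | 82.1% |

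At 18 per group the shortfall is 80 − 77.7 = 2.3 points. Taking the difference as 20 points instead of 19.89 raises power only to 78.1%. The difference detectable with 80% power at 18 per group is 20.5 points, which is 20.5/66.3 = 30.9% relative.

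**Step 4: power of the Mann-Whitney test.** Simulating 20,000 trials with normal data and the same means and SD gives about 75% at 18 per group. Normality is an assumption; the protocol gives no distribution for time in range.

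**Step 5: is there slack in enrolment?** 2 × 18 = 36, and 36/0.9 = 40 exactly. Conversely, 40 × 0.9 = 36 evaluable. The planned loss uses all four extra women.

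**The case against.** The protocol's numbers do reproduce: 18 comes from a standard textbook formula, and 40 follows exactly from 18 and 10% loss. That stands, and this should not be called an arithmetic error. An exact t-based calculation differs by only one or two women per group.

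A reader who sees 18.002 might infer that the sponsor wrongly rounded down and that this is why 80% is missed. The documents do not support that. Section 8 shows no unrounded figure and no rounding step, ordinary rounded inputs give 17.98 and round up to 18, and the rounding would cost only 0.005 points. Going to 19 would still give 79.97% by the t-test.

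The shortfall is also small beside the uncertainty in the inputs. At 18 per group and 19.89 points, t-test power is 80% if the SD is 20.7, 82.6% if it is 20 and 75% if it is 22. A change of 0.6 points in an SD taken from an external cohort cancels the gap. This stands as a reason for low severity, and against reading the trial as seriously underpowered for its stated target. It does not make the stated figure right, because Section 8 gives one SD and one power, and the two do not match under either named test.

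Finally, Section 9 does not commit the primary outcome to the t-test, and a statistical analysis plan that is not at hand may settle the choice. That is fair, but the choice does not rescue the 80%: the alternative test has lower power on normal data.

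**Conclusion.** The point holds as a minor one. On the protocol's own inputs, 18 evaluable women per group give about 78% power with a two-sided t-test and about 75% with a Mann-Whitney test, not 80%. Enrolling 40 leaves no margin once the stated loss occurs. Essentially the whole t-test gap comes from applying the normal approximation at a small sample size.

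The conclusion rests on three assumptions: the 30% is relative and alpha is two-sided (together the reading that reproduces 18), and the data are normal for both power figures. If alpha were one-sided, t-test power at 18 per group would be 86.4% and there would be no shortfall, but the z formula would then have given 15, not 18.

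**What to change.** Keep enrolment at 40 and restate Section 8 along these lines: *18 evaluable women per group give about 78% power (two-sided t-test, alpha 0.05) for a difference of 19.9 percentage points in time in range (a 30% relative improvement on 66.3%, SD 21.3), or 80% power for a difference of 20.5 points.* This also settles in the text that the 30% is relative and that the test is two-sided.

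The cost is a change of protocol wording only; design, enrolment and analysis stay as they are. The downside is that the stated power becomes slightly less favourable. For comparison, holding to at least 80% by the t-test for 19.89 points would take 20 evaluable per group: 20/0.9 = 22.2, so 23 per group and 46 in total. A gap of 2.3 points does not call for that.

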Optimization of glucose levels in pregnancy can reduce the risk of several adverse outcomes, which include miscarriage, congenital birth defects, macrosomia, intrauterine fetal demise, and neonatal morbidity ². Traditionally in pregnancy, patients with diabetes would monitor blood glucose levels four times daily: fasting and then 1- or 2-hours postprandial. However, more recently, continuous glucose monitoring (CGM) has become more popular and readily available. In a cohort of patients using CGM, Bartal et al. found that the proportion of the time glucose levels were within what is considered acceptable range, referred to as time in range was associated with neonatal outcomes ³. Specifically, patients whose time in range was below 70% had worse neonatal outcomes than those with time in range at or above 70%.

We hypothesize that post-prandial walking will improve time in range on continuous glucose monitoring, as well as maternal and neonatal outcomes in pregnant patients with Type 2 diabetes. As an initial step in testing this hypothesis, we will conduct a randomized controlled trial to limit bias in evaluating these hypotheses. A FitBit will be provided to both groups to assess adherence to the walking regimen.

Each year, approximately 400 pregnant women with Type 2 diabetes are followed at Eastern Virginia Medical School Maternal Fetal Medicine. This would be the first randomized-controlled trial focusing on post-prandial walking utilizing continuous glucose monitoring and FitBit data in this US patient population.

2. Specific aims:

Aim 1. To examine the effect of post-prandial walking on time in range on CGM in pregnant patients with Type 2 diabetes

3. Study design:

We propose a randomized controlled trial of women with singleton pregnancies who present with a diagnosis of pre-gestational Type 2 diabetes. The participants will be randomized to the intervention group (post-prandial walks + standard care) or control group (standard care alone which includes the usual counseling regarding activity) in a 1:1 ratio. The participant will be randomized by a number-generating

computer software after recruitment at the gestational diabetes education class. All participants will receive a continuous glucose monitor and basic model FitBit for use and data collection.

Inclusion criteria

- Singleton gestation
- Known diagnosis of Type 2 diabetes OR meets new diagnosis of Type 2 diabetes in the first trimester (up through 13 weeks and 6 days)⁹

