- Age ≥ 18 and <50 years
- Gestational age <32 weeks 0 days gestation

Exclusion criteria

- Non-English as primary language.
- Inability to participate in 20 minutes of walking at a time
- Known or suspected fetal anomaly or aneuploidy
- Prisoners
- Management of diabetes outside of Eastern Virginia Medical School Maternal Fetal Medicine

Because we are a tertiary care center, some individuals may be seen at several different time points in the pregnancy at time of recruitment. All of these participants can be included for recruitment until 32 weeks 0 days gestation.

3.1 Postprandial walking:

Post-prandial walking group

Participants will be instructed to walk specifically for 20 minutes after each meal (breakfast, lunch, and dinner).

Control group

Participants will receive the usual counseling regarding physical activity, which does not include post-prandial walking.

Both groups

All participants will be encouraged to continue exercise per the U.S. Department of Health and Human Services Physical Activity Guidelines for Americans and the American College of Obstetricians and Gynecologists recommendations, which includes at least 150 minutes of moderate intensity aerobic activity per week during pregnancy. Given these recommendations, post-prandial walking is minimal risk to the patient and is an activity that patients may choose to do even outside of this study.

Both groups will have a fasting blood draw and urine sample at enrollment and between 34-36 weeks gestation in the outpatient setting, typically less than 25cc blood, to test for metabolomics.

Both groups will also have an estimation of body composition at enrollment and between 34-36 weeks gestation using bioelectrical impedance analysis (BIA), which introduces (non-invasively) a current into the body passing through a source electrode and a detector electrode, located on both hands and feet. BIA measures Resistance and Reactance and their vector relationship Impedance. Based on predictive equation, BIA estimates fat mass, fat-free mass, lean soft tissue, total body, intracellular, extracellular water, and phase angle. There are no known risks or discomforts related to the BIA. Minor discomfort is associated with the placement and removal of the electrodes on the skin.

4. Procedures:

4.1 Recruitment and Screening:

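### Section 9 gives the enrolment values of body composition and metabolomic markers no stated role; adjusting for them would usually sharpen these secondary comparisons at almost no cost

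*Protocol*

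**What the plan says.** Section 9 (Statistical analysis) has two sentences. After descriptive statistics and tests for categorical variables, it states that "the Student t-test or Man-Whitney U test will be used to compare numerical variables". It names no covariate, change score, paired analysis or repeated-measures model, and no other section does.

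Section 6 (Outcomes) makes both sets of measurements outcomes: "Other secondary outcomes will include metabolomic markers collected from the urine and blood, as well as body composition data". Neither is defined there as a change from enrolment.

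Section 3.1 schedules each of them twice. For bioimpedance: "Both groups will also have an estimation of body composition at enrollment and between 34-36 weeks gestation". For the samples: "Both groups will have a fasting blood draw and urine sample at enrollment and between 34-36 weeks gestation". Section 7 repeats the blood schedule: "There will be two blood draws: at enrollment and again between 34 and 36 weeks gestation".

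Section 3 lets women enter at very different stages: "some individuals may be seen at several different time points in the pregnancy at time of recruitment", and "All of these participants can be included for recruitment until 32 weeks 0 days gestation".

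On the order of events, Section 3 places randomisation by "computer software after recruitment at the gestational diabetes education class". Section 7 has the samples taken at a clinic visit that is already booked. Neither says whether the enrolment measurements come before the woman learns her arm.

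**The concern.** The trial collects an enrolment value for these outcomes in every woman, and the one stated method does not say what to do with it. Section 9 can be followed in two ways: a two-sample test on the 34-36 week values, which ignores the enrolment value, or a two-sample test on the change, which uses it with a fixed weight of one. These two analyses differ in precision, sometimes by a lot, and the choice between them is open. Over most of the plausible range, both are less precise than a comparison of final values adjusted for the enrolment value.

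At this size that matters. With about 18 women per arm, a comparison of final values can detect only a difference of nearly one standard deviation, and chance imbalance in the enrolment values is likely to be material. What is at stake is the width of the intervals for body composition and the metabolomic markers.

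**Working it through.** **Number of women.** Section 8 takes time in range of 66.3% with SD 21.3%, a 30% relative improvement (0.30 × 66.3 = 19.89 points), 80% power and alpha 0.05. Two-sided, n = 2 × [21.3 × (1.960 + 0.842) / 19.89]² = 18.00 per group, which agrees with the stated 18. Allowing 10% loss, 36 / 0.90 = 40, as stated. That calculation concerns the primary outcome; here it only supplies n = 18 evaluable women per arm.

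**Assumptions.** The documents give no correlation r between the enrolment and 34-36 week values, so r = 0.3, 0.5, 0.7 and 0.9 are shown. The SD is taken as equal at both times, with two-sided alpha 0.05, 80% power and the noncentral t distribution.

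**Formulas**, in units of one SD:
- Final values (34 df): 2.884 × √(2/18) = 0.961.
- Changes (34 df): 0.961 × √(2(1 − r)).
- ANCOVA on the enrolment value (33 df): 2.886 × √(2/18) × √(1 − r²) × √(1 + 1/32) = 0.977 × √(1 − r²). The last factor is the average cost of estimating the slope.

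| r | Final values | Changes | ANCOVA | ANCOVA below final | ANCOVA below changes |
|---|---|---|---|---|---|
| 0.3 | 0.961 | 1.137 | 0.932 | 3% | 18% |
| 0.5 | 0.961 | 0.961 | 0.846 | 12% | 12% |
| 0.7 | 0.961 | 0.745 | 0.698 | 27% | 6% |
| 0.9 | 0.961 | 0.430 | 0.426 | 56% | 1% |

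ANCOVA breaks even with final values at r = 0.179 and with changes at r = 0.936. Outside those points it loses slightly.

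**Stricter alpha.** These are single-test figures and do not describe a whole metabolomic panel. The relative gain hardly depends on alpha: at 0.001 the detectable difference is 1.497 on final values and 1.454, 1.320, 1.089 and 0.665 with ANCOVA, again 3%, 12%, 27% and 56% smaller.

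**Varying interval between measurements.** Simulation, 20,000 trials per scenario, with enrolment assumed uniform over 8-32 weeks, the final value at 35 weeks, and r falling linearly as the interval lengthens. Mean 95% interval half-width in SD:

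| r, shortest to longest interval | Final | Changes | ANCOVA | ANCOVA + gestational age |
|---|---|---|---|---|
| 0.9 to 0.5 | 0.672 | 0.520 | 0.487 | 0.495 |
| 0.8 to 0.3 | 0.672 | 0.637 | 0.570 | 0.579 |
| 0.6 to 0.1 | 0.673 | 0.767 | 0.640 | 0.651 |

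ANCOVA intervals are 28%, 15% and 5% narrower than final values, and 6%, 11% and 17% narrower than changes. If the marker also drifts with gestation (assumed 1.44 SD over 24 weeks), the half-width for changes rises to 0.590, 0.696 and 0.814, and for ANCOVA to 0.520, 0.588 and 0.646. Type I error was 0.048 to 0.052 throughout. In a run of the change analysis with the drift and no true effect (r 0.9 to 0.5), the mean difference between arms was 0.002 SD. The varying interval adds variance, not bias.

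**Gestational age at enrolment as a second covariate.** The detectable difference becomes 0.948, 0.861, 0.710 and 0.433, which is 1.7% larger than with the enrolment value alone if gestational age explains nothing. It pays only if its residual correlation with the outcome exceeds about 0.18. With the assumed drift, its half-widths were 0.495, 0.579 and 0.650: better than ANCOVA alone in the first two scenarios, marginally worse in the third.

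**The case against.** The strongest reply is that nothing in Section 9 is wrong. It is a short, generic statement covering a long list of outcomes. It does not forbid adjustment, and covariates and transformations for secondary laboratory outcomes are often settled in an SAP, which may exist here. That limits the weight of the point but does not remove it: the protocol does state a method for numerical variables, and a better one is available from data it already schedules. If an SAP adjusts, Section 9 should be brought into line with it.

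Several stronger readings are tempting and are not supported:
- A reader might infer that the enrolment values are shut out of the analysis. They are not: a t-test on the change would comply with Section 9 and would use them. They have no *stated* role.
- A reader might infer that, because women enrol at different stages, raw changes confuse the walking effect with length of pregnancy. Randomisation balances gestational age at enrolment on average, so the comparison between arms stays unbiased and can only become noisier.
- A reader might take 27% to 56% as the loss. Those figures need a high correlation and the final-values reading. At the same correlations, the changes reading loses only 6% to 1%.
- A reader might extend the point to time in range. The protocol schedules no equivalent enrolment value for it.

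It also stands that the size of the gain rests on a correlation the documents do not give, and that the remedy presumes enrolment measurements taken before the allocation is known.

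**Conclusion.** The point holds as a matter of efficiency, for the body composition and metabolomic outcomes only. An unadjusted two-sample test is valid here, but whichever way it is applied, it is less precise than ANCOVA on the enrolment value for correlations between about 0.18 and 0.94. The gain may be trivial or large depending on the true correlation and on which reading of Section 9 is meant. No conclusion on the primary outcome changes. This is something for the sponsor to consider, held with medium confidence. It assumes 18 evaluable women per arm, equal SDs at the two times, a roughly linear relation between the two values, and an enrolment value that is a true baseline.

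**What to change.** Add to Section 9, before any outcome data are seen: *Body composition and metabolomic outcomes at 34-36 weeks will be compared between arms by ANCOVA adjusted for the enrolment value, reporting the mean difference with its 95% confidence interval; skewed markers will be log-transformed.* Gestational age at enrolment, which is known from eligibility, is an optional second covariate.

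Confirm that the enrolment blood, urine and bioimpedance measurements are taken before the allocation is disclosed, and say so in the protocol. If they are not, the enrolment value is not a true baseline and the order of enrolment procedures would need to change first.

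The cost is one or two sentences, with no extra women, samples or visits, plus a small procedural change if that order is currently reversed. The statistical price is one degree of freedom and a slight loss of precision if the correlation proves very low (or, against changes, very high).
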